7.1 Recruitment

Potential participants will be recruited through academic and NIHR clinical trials sites.

Information about the study will be disseminated as widely as possible amongst the potentially eligible population. Each site will record the number of mail out letters they send out and information will be collected on a pre-screening log about all women who are approached by a member of the research team to discuss the study. The information collected will include the date they were approached, their age and whether they are willing to consider participation in the study. If women are not willing to consider participation in the study the reason for this will be collected where possible.

7.1.1 Participant identification

Women may be identified in a number of ways according to local arrangements. Some may be identified when they attend hospital or community appointments and approached about the study, others may be identified from hospital lists of women due to attend for antenatal care and have information sent out to them. In the latter circumstance this identification will be performed by members of the clinical team - the research team will not have access to identifiable information without consent. After a woman has received information about the study at any point from the time of the booking appointment she may agree to being contacted by a member of the study team. This would require her to complete the information on the invitation letter and completion of this slip will be assumed to be consent to be contacted.

The following means of approaching women may be used at sites:

- Information sent through the post/email about the study
- Information provided directly when women attend for a community or hospital appointment
- Women seeing a leaflet or poster about the study when attending a hospital appointment
- Women seeing information about the study on an institutional website (both hospital and university), on social media or in a press release

Women who have signed up to the NIHR Vaccine registry may be approached directly about the study and provided with a link with further information.

Women who are potentially interested in participating in the study will be directed, via a link, to the trial website which will provide further information about the trial (including the participant information sheet and the inclusion and exclusion criteria).

7.1.2 Screening

The trial website will provide further information about the trial and direct potential participants to a series of screening questions. These questions will assess their suitability for inclusion (against the trial inclusion and exclusion criteria) as well as their geographic location. If they are deemed eligible for inclusion then the appropriate local recruitment site will be informed and will then make direct contact with the potential participant.

The eligibility of an individual to participate in this study will also be assessed by any appropriately trained and delegated member of the local research team. After signing the informed consent, participants may be screened and enrolled at Visit 1. During the screening period, nose/throat samples

may be taken to detect SARS-CoV-2 by PCR, if the participant has any COVID-19 symptoms or significant exposure history.

7.1.3 Expenses and Benefits

Volunteers will be compensated for their time, the inconvenience of having blood tests and procedures, and their travel expenses. The total amount compensated will depend on the exact number of visits, and whether any repeat or additional visits are necessary. For all trial visits compensation will be calculated according to the following:

- Travel expenses: £15 per visit (not applicable if home visit)
- Inconvenience of blood tests: £10 per blood donation
- Time required for visit: £20 per visit

7.2 Consent

The Principal Investigator (PI) retains overall responsibility for the conduct of research at their site, this includes the taking of informed consent of participants at their site. They must ensure that any person delegated responsibility to participate in the informed consent process is duly authorised, trained and competent to participate according to the ethically approved protocol, principles of Good Clinical Practice (GCP) and Declaration of Helsinki. If delegation of consent is acceptable then details should be provided.

Informed consent must be obtained prior to the participant undergoing procedures that are specifically for the purposes of the trial and are out-with standard routine care at the participating site (including the collection of identifiable participant data unless the trial has prior approval from the Confidentiality Advisory Group (CAG) and the Research Ethics Committee (REC))

The right of a participant to refuse participation without giving reasons must be respected.

The participant must remain free to withdraw at any time from the trial without giving reasons and without prejudicing her further treatment and must be provided with a contact point where she may obtain further information about the trial. Data and samples collected up to the point of withdrawal can only be used after withdrawal if the participant has consented for this. Any intention to utilise such data should be outlined in the consent literature. Where a participant is required to re-consent or new information is required to be provided to a participant it is the responsibility of the PI to ensure this is done in a timely manner.

The PI takes responsibility for ensuring that all vulnerable participants are protected and participate voluntarily in an environment free from coercion or undue influence.

The consent process will involve:

- discussion between the potential participant and a clinical member of the study team (research midwife / research nurse / research doctor) knowledgeable about the research, the nature and objectives of the trial and possible risks associated with their participation
- the presentation of written material (participant information leaflet (PIS) and consent document which is approved by the REC and in compliance with GCP, local regulatory requirements and legal requirements
- the opportunity for potential participants to ask questions
- assessment of capacity. Participants must be capable of giving consent for themselves. A capable person will:
 - understand the purpose and nature of the research
 - understand what the research involves, its benefits (or lack of benefits), risks and burdens
 - understand the alternatives to taking part
 - be able to retain the information long enough to make an effective decision.
 - be able to make a free choice
 - be capable of making this particular decision at the time it needs to be made

A copy of the signed Informed Consent Form (ICF) along with a copy of the most recent approved Patient Information Sheet (PIS) will be given to the study participant. An original signed and dated consent form will be placed in the participant's study folder and a copy will be sent to the GP. An entry will be made in the participant's handheld medical notes along with a copy of their signed consent form documenting her participation in the study.

7.2.1 Additional consent provisions for collection and use of participant data and biological specimens in ancillary studies, if applicable

Participants will be asked if they agree to sample collection (maternal and infant) and to the retention of any remaining samples for future related, ethically approved research. Consent to this will not be required for participation in the main study. With the participant's informed consent, any leftover samples will be frozen and transferred to St George's, University of London at the end of the study. If a subject elects not to permit this, all of that participant's leftover samples will be discarded at the end of the trial.

Participants at St George's University Hospitals NHS Foundation Trust and one other site (to be selected) will be asked if they are willing to take part in an additional study investigating functional immunity in breast milk following vaccination in pregnancy. If they are willing to participate in this aspect of the study, they will be asked to provide consent for this at the time of initial consent. Participation in this study is optional and not wishing to take part in this aspect of the study will not affect their participation in the rest of the study. Samples for this study will be identified with the study identification number. As with the main study participants will be informed that if they withdraw from the study their data and samples would continue to be used.

7.3 The randomisation scheme

7.3.1 Method of implementing the randomisation/allocation sequence

For the main study (cohort 1 and cohort 2), computer generated randomisation lists will be prepared by the study statistician. Participants will be randomised 1:1:1:1:1 for each of the vaccine groups (Pfizer / Moderna / Novavax) at "short" and "long" prime-boost intervals, using block randomisation. Random block sizes of 6 or 12 will be used. The randomisation will be stratified by the study cohort and study sites.

For the sub-study of cohort 3, participants will be randomised 1:1:1 to the study vaccines (Pfizer / Moderna / Novavax) using block randomisation. Random block sizes of 3 or 6 will be used, and the randomisation will be stratified by study sites. The sub-study of cohort 4 will be an open label study, women primed with a COVID-19 vaccine will be randomised to a boost vaccine (of the same type) before or after 26 weeks of gestational age on a 1:1 basis. Random block sizes of 2 or 4 will be used and stratified by study sites.

The study design is "adaptive" in that new COVID-19 vaccines may be included as soon as they are licensed. Randomisation will be adjusted accordingly. The allocation ratio will adaptively evolve over the course of the trial and will be fully described in the Interim Analysis.

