Recruitment window (wk)	Total n=200 for each vaccine for cohort 1 + cohort 2	Day 0	Short 4-6 wk	Long 8 wk-12wks*
24 0/7 – 27 6/7		Vaccine A	- **	Vaccine A
		Vaccine A	Vaccine A	- **
		Vaccine B	- **	Vaccine B
		Vaccine B	Vaccine B	- **
		Vaccine C	- **	Vaccine C
		Vaccine C	Vaccine C	- **

* “Long” dose must be given by 36 weeks’ gestation

** dTaP/IPV should be given by 32 weeks’ gestation with an interval of at least 1 week before / after receipt of COVID-19 vaccine

Table 3. Cohort 3.

Recruitment window (wk)	Total n=100	Day 0	Post delivery (4-12 weeks but given after delivery)*
28 0/7 – 34 0/7		Vaccine A	Vaccine A
		Vaccine B	Vaccine B
		Vaccine C	Vaccine C

* Booster dose should be given as soon as possible after delivery

** if require dTaP/IPV, it should be given by 32 weeks' gestation and with an interval of at least 1 week before / after receipt of COVID-19 vaccine

Table 4. Cohort 4.

Recruitment window (wk)	Total n= 100	Boost dose <26 weeks	Boost dose ≥26 weeks
13 0/7 – 34 0/7		Vaccine A/B/C/D*	Vaccine A/B/C/D*

*Same vaccine as given pre-pregnancy / first trimester (0 0/7 – 12 6/7 gestational weeks)

** if require dTaP/IPV, it should be given by 32 weeks' gestation and with an interval of at least 1 week before / after receipt of COVID-19 vaccine

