7 TRIAL PROCEDURES

Screening + study visit 1 (Maternal)

This visit will take place between 13 0/7 – 27 6/7 gestational weeks (for the earlier gestational weeks group) or between 28 0/7 – 34 0/7 gestational weeks (for the later gestational weeks group) at the participating institution. Eligibility will be confirmed, the study will be discussed in more detail and women will be asked to sign a consent form. They will then be asked about demographic details (including NHS number), past medical history, receipt of any prior dose of a COVID-19 vaccine, details of the current pregnancy including the results of antenatal screening and scans to ensure that they are eligible for the study. The participant's antenatal medical notes will be reviewed. Details will be collected about concomitant medication. A physical examination will be performed, and vital signs, height and weight will be recorded. Immunogenicity blood samples will be obtained.

Cohort 1, 2, 3: Participants will be randomised to a single group to receive one type of COVID-19 vaccine with the first dose to be given at visit 1.

Cohort 4: Participants will receive the same vaccine as given pre-pregnancy or during their first trimester (0 0/7 – 12 6/7 gestational weeks) and randomised to either receiving the booster dose before or after 26 weeks' gestation.

Vaccination will be given by members of the study team who are trained and experienced in vaccine administration and in emergency procedures in the event of an allergic reaction. They will have access to emergency medication and equipment. The vaccinations will be given according to the advice in the “Green Book” and the Summary of Product Characteristics (SmPC). An eDiary will be set up for the participant and they will be given instructions to complete the diary regularly for 28 days following vaccination. The participant will be observed for a period of 20 minutes following vaccination to assess for allergic adverse events.

Study visit 2 (Maternal) all cohorts

14 days (10 days – 21 days) after first vaccination review by telephone call.

- SAE / AESI / MAAE check
- Concomitant medication check
- eDiary review

Study visit 3 (Maternal) all cohorts

Day 28-42 following the first vaccination at the participating institution.

- SAE / AESI / MAAE check
- Concomitant medication check
- eDiary review
- Targeted physical examination if indicated
- Immunogenicity blood samples will be collected
- **Cohort 1.**
 - Vital signs pre-vaccination

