Cohort 3 Visit Schedule - Pregnant women enrolled between 28 0/7 - 34 0/7 gestational weeks

	PRENATAL						DELIVERY	POSTNATAL				
	Screening + V1	V2	V3	V4	V5	V6	V7	V8 ^b	V9 ^c	V10	V11	V12
Study timeline	D0	D14	D28-42	No visit in this cohort	No visit in this cohort	No visit in this cohort	Delivery	Delivery up to 7 days (where possible)	Delivery +14 days (where possible)	Delivery +28-42 days	Delivery +182 days (+/- 14 days)	Delivery +364 days (+/- 14 days)
Study window	D0	Day 10-21 post V1 (phone)	Day 28-42 post V1				N/A	0 - 7 days post delivery	Day 12-16 post delivery (phone)	Day 28-42 post delivery	Day 168-196 post delivery (phone)	Day 349-379 post delivery
Informed consent	X											
Screening bloods - maternal (HIV, Hep B, Syphilis) from routine prenatal visits	X (routine)											
Ultrasound dating and anomaly scan from routine prenatal visit	X (routine)											
Medical History	X											
Physical examination - maternal	X		(X)				(X)	(X)		(X)		
Vital signs, height and weight	X							X				
Vaccination	X							X				
COVID-19 immunogenicity bloods - maternal	X		X				X			X		X
eDiary review		X	X						X	X		
SAE/AES/Medically attended AE check		X	X					X	X	X	X	X
Concomitant medication check	X	X	X					X	X	X	X	X
Physical examination - infant							X					X
COVID-19 immunogenicity bloods - infant										X ^a		
Neurodevelopmental assessment (Ages & Stages questionnaire) - infant												X
Cord blood sample (selected sites)							X					
Colostrum / Breast milk sample (selected sites)								X				

^a Cohort 3 will have infant and maternal blood samples taken at 28-42 days post-delivery

^b V8 only for breast milk sub-study sites or Cohort 3

^c V9 is a telephone call review except for breast milk sub-study sites (in brackets) - as required

Cohort 4 Visit Schedule - Pregnant women enrolled between 13 0/7 - 27 6/7 gestational weeks and received a COVID-19 vaccine before pregnancy or during first trimester (0 0/7 - 12 6/7 gestational weeks)

	PRENATAL					DELIVERY	POSTNATAL					
	Screening ^a	V1	V2	V3	V4 + V5	V6 ^b	V7	V8 ^c	V9 ^d	V10	V11	V12
Study timeline	Screening	D0	D14	D28-42	No visit in this cohort	D112 - 140	Delivery	Delivery to 7 days (where possible)	Delivery +14 days (where possible)	Delivery +28-42 days OR 70-84 days	D182 (+/- 14 days)	D364 (+/- 14 days)

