Study window		<26 weeks gestation OR >26 weeks gestation	Day 10-21 post V1 (phone)	Day 28-42 post V1		Day 112 - 140 post V1	N/A	0 - 7 days post delivery (phone)	Day 12-16 post delivery (phone)	Day 28-42 OR 70-84 post delivery	Day 168-196 post delivery (phone)	Day 349-379 post delivery
Informed consent	X											
Screening bloods - maternal (HIV, Hep B, Syphilis) from routine prenatal visits	X (routine)											
Ultrasound dating and anomaly scan from routine prenatal visit	X (routine)											
Medical History	X											
Physical examination - maternal	X	(X)		(X)		(X)	(X)			(X)		
Vital signs, height and weight	X	X										
Vaccination	X	X										
COVID-19 immunogenicity bloods - maternal		X		X		X	X			X		X
eDiary review			X	X		X						
SAE/AESI/Medically attended AE check		X	X	X		X		X	X	X	X	X
Concomitant medication check	X	X	X	X		X		X	X	X	X	X
Physical examination - infant							X					X
COVID-19 immunogenicity bloods - infant										X ^e		
Neurodevelopmental assessment (Ages & Stages questionnaire) - infant												X
Cord blood sample (selected sites)							X					
Colostrum / Breast milk sample (selected sites)								X	X			

^a Screening and V1 can be done at the same time if randomisation to vaccination schedule allows.

^b V6 will take place if the window starts before their due date.

^c V8 only for breast milk sub-study sites or Cohort 3

^d V9 is a telephone call review except for breast milk sub-study sites

^e Infant is randomised at V9 to blood sampling at 4-6 weeks or 10-12 weeks after birth except cohort 3 (cohort 3 will have infant and maternal blood samples taken at 28-42 days post-delivery).

(in brackets) - as required

Cohort 1 and 2 Laboratory Sampling Schedule - Pregnant women enrolled between 13 0/7 - 27 6/7 gestational weeks

	PRENATAL						DELIVERY			POSTNATAL			
	Screening + V1	V2	V3	V4 ^b	V5 ^b	V6 ^c	V7	V8	V9	V10 ^d	V11	V12	
Study timeline	D0	D14	D28-42	D56-84	D84-112	D112 - 140	Delivery	Delivery up to 7 days	Delivery +14 days	Delivery + 28-42 days OR 70-84 days	D182 (+/- 14 days)	D364 (+/- 14 days)	
Study window	D0	Day 10-21 post V1	Day 28-42 post V1	Day 56-84 post V1	Day 28-42 post V3	Day 56-84 post second COVID vaccine	N/A	0 - 7 days post delivery	Day 12-16 post delivery	Day 28-42 OR 70-84 post delivery	Day 168-196 post delivery	Day 349-379 post delivery	
Vaccination	X	X ^e	X ^e	X ^e	X	X	X			X			

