Cohort 3 Laboratory Sampling Schedule - Pregnant women enrolled between 28 0/7 - 34 6/7 gestational weeks

	PRENATAL					DELIVERY		POSTNATAL				
	V1	V2	V3	V4	V5	V6	V7	V8	V9	V10**	V11	V12
Study timeline	Screening + V1	D14	D28	No visit in this cohort	No visit in this cohort	No visit in this cohort	Delivery	Delivery up to 7 days	Delivery +14 day	Delivery + 28-42 days	D182 (+/- 14 days)	D364 (+/- 14 days)
Study window	D0	Day 10-21 post V1	Day 28 post V1				N/A	0 - 7 days post-delivery	Day 12-16 post-delivery	Day 28-42 post-delivery	Day 168-196 post-delivery	Day 349-379 post-delivery
Vaccination	X							X				
COVID-19 immunogenicity bloods - maternal	X Nexelis Anti-spike IgG PHE ADCC		X Nexelis Anti-spike IgG PHE Neutralising Abs ADCC				X Nexelis Anti-spike IgG PHE Anti-nucleocapsid IgG Neutralising Abs ADCC			X Nexelis Anti-spike IgG		X Nexelis Anti-spike IgG PHE ADCC
Cord blood sample (at selected sites)	IMMUNOTEC ELISpot & ICS (7 sites)		IMMUNOTEC ELISpot & ICS (7 sites)				SGUL Lab ELISpot & ICS (2 sites)					IMMUNOTEC ELISpot & ICS (7 sites)
Colostrum / Breast milk sample (at selected sites)							X Nexelis Anti-spike IgG PHE Anti-nucleocapsid IgG SGUL Lab ELISpot & ICS			X SGUL Lab Anti-spike IgG ELISpot + ICS		
COVID-19 immunogenicity bloods - infant										X Nexelis Anti-spike IgG PHE Anti-nucleocapsid IgG		
Sample volumes (+ blood bottles)	Maternal: Up to 50mls (20mls red, 30mls green/ Lihsep)		Maternal: Up to 20mls (20mls red)				Maternal: Up to 50mls (20mls red, 30mls green/ Lihsep) Cord blood: up to 30mls	Colostrum: 1-2mls	Breast milk: 2-5mls	Maternal: Up to 20mls (20mls red) Infant: up to 5mls		Maternal: Up to 50mls (20mls red, 30mls green/ Lihsep)

** infant plus maternal blood samples to be taken at 28-42 days post-delivery

Cohort 4 Prenatal Laboratory Sampling Schedule - Pregnant women enrolled between 13 0/7 - 27 6/7 gestational weeks and received a COVID-19 vaccine before pregnancy or during first trimester (0 0/7 - 12 6/7 gestational weeks)

	PRENATAL							DELIVERY				POSTNATAL			
	Screening	V1	V2	V3	V4	V5	V6	V7	V8	V9	V10**	V11	V12		
Study timeline	Screening	D0	Day 14	D28-42	No visit in this cohort	No visit in this cohort	D112 - 140	Delivery	Delivery up to 7 days	Delivery +14 days	Delivery + 28-42 days OR 70-84 days	D182 (+/- 14 days)	D364 (+/- 14 days)		

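### Cohort 4 randomises every woman to a boost before or after 26 weeks, yet enrols women already past 26 weeks, so some draw an arm they cannot receive

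*Protocol*

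**What the plan says.** Four places in the protocol bear on this.

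- **Section 7.3.1** describes cohort 4 as open label: "women primed with a COVID-19 vaccine will be randomised to a boost vaccine (of the same type) before or after 26 weeks of gestational age". The ratio is 1:1, and "Random block sizes of 2 or 4 will be used and stratified by study sites". Gestation is neither a stratum nor a condition for being randomised.
- **Section 7, visit 1**, repeats the rule for cohort 4 as a whole. Women get the vaccine they had before and are "randomised to either receiving the booster dose before or after 26 weeks" of gestation, with no exception for those already beyond that point.
- **Section 2, Table 4**, labels one arm "Boost dose <26 weeks" and the other as 26 weeks or later. Its recruitment window is 13 0/7 to 34 0/7, in a single row.
- **Section 16.3, Appendix 4**, gives a different window twice: "Cohort 4 Visit Schedule - Pregnant women enrolled between 13 0/7 - 27 6/7 gestational weeks" and "Cohort 4 Prenatal Laboratory Sampling Schedule - Pregnant women enrolled between 13 0/7 - 27 6/7 gestational weeks". Footnote a to the visit schedule adds: "Screening and V1 can be done at the same time if randomisation to vaccination schedule allows".

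Section 10.1 makes cohort 4 exploratory, with up to 100 women and no formal sample size calculation.

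**The concern.** Both windows extend beyond the gestation that separates the arms. A woman below 26 weeks can receive either allocation, waiting if she draws the later one. A woman at 26 0/7 or later can receive only one, yet the stated rule still gives her a one-in-two chance of the other.

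The protocol does not say what then happens, and each obvious course has a price:

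- **Analysed as allocated.** Randomisation is preserved, but late enrolees are boosted after 26 weeks in both arms, so the contrast is diluted.
- **Moved to the later arm and analysed as boosted.** The later arm then holds women who could never have been in the earlier one, so the contrast is confounded with gestation at presentation.

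Each such allocation is also a departure from protocol built into the design, while section 13.5 treats frequently recurring deviations as unacceptable.

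**Working it through.** The protocol states no figure for undeliverable allocations, so there is none to reproduce. The check compares each window with the 26-week boundary and then sizes the overlap.

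**Inputs.** Arm boundary 26 0/7 (Table 4). Ratio 1:1 (section 7.3.1). N = 100 (section 10.1, upper limit). Windows 13 0/7–27 6/7 (Appendix 4) and 13 0/7–34 0/7 (Table 4). Even enrolment over the window is my assumption.

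**Formulas.** Let f be the share enrolled at 26 0/7 or later.

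- f = days at or past 26 0/7 ÷ days in the window, both ends counted
- Undeliverable allocations = N × f ÷ 2
- As allocated, share of the contrast kept = 1 − f, because late enrolees contribute no difference between arms
- As boosted, earlier arm = N(1 − f) ÷ 2; later arm = N(1 − f) ÷ 2 + Nf
- As boosted, share of the later arm that could never have been in the earlier one = Nf ÷ later arm

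| | Window to 27 6/7 | Window to 34 0/7 |
|---|---|---|
| f | 14/105 = 13.3% | 57/148 = 38.5% |
| Undeliverable per 100 | 13.3/2 = 6.7 | 38.5/2 = 19.3 |
| Contrast kept, as allocated | 86.7% | 61.5% |
| Earlier arm, as boosted | 86.7/2 = 43.3 | 61.5/2 = 30.7 |
| Later arm, as boosted | 43.3 + 13.3 = 56.7 | 30.7 + 38.5 = 69.3 |
| Later arm never eligible for earlier | 13.3/56.7 = 23.5% | 38.5/69.3 = 55.6% |

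Counting whole weeks changes little: 2/15 = 13.3% and 8/21 = 38.1%.

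**Without even enrolment.** If 5% to 50% of women enrol at 26 0/7 or later, 2.5 to 25 of 100 allocations are undeliverable. The number reaches zero only if nobody enrols that late.

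**Does any other text close the gap?**

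- Footnote a allows V1 to be held after screening. That serves a woman below 26 weeks who draws the later arm. It cannot help one already past 26 weeks, and it presupposes that she has been randomised.
- Section 4 says allocation depends on gestation at recruitment, but it points to Tables 1–4, and Table 4 does not split by gestation.
- Section 6.1 sets 34 0/7 as the limit on the day of vaccination. If Table 4 was meant that way, its column is mislabelled, and women from 26 0/7 to 27 6/7 are still randomised.

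**The case against.** The case on the other side concedes the conflict and contests its weight.

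- **No objective names a before/after-26-week contrast.** The cohort 4 objectives in section 3.2.1 concern booster response overall and boosts given at 28–34 weeks. The secondary objective on gestational age at vaccination does not refer to randomised arm. This is true, and the link to that secondary objective is indirect. But a 1:1 allocation on timing has no evident purpose other than to support that contrast.
- **The 34 0/7 window may be a labelling slip.** Enrolment to 27 6/7 with vaccination to 34 0/7 fits section 6.1, both Appendix 4 schedules and the 28–34 week objectives. This is a fair reading, so the 34 0/7 figures are an upper end.
- **Enrolment probably leans early.** These women had their first dose by 12 6/7 weeks, so at 26 0/7 they are at least 13 weeks past it. Section 1 puts routine second doses at 4 to 12 weeks, so many would be boosted before 26 weeks. About 7 in 100 may therefore overstate the problem under the 27 6/7 window. This affects the size only.
- **The analysis plan can settle the analysis set.** It can choose between the two analyses. It cannot change who is randomised, which the protocol fixes.
- **Cohort 4 is exploratory and open label.** This stands, and it limits the consequences.

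**Conclusion.** The concern holds. As written, the cohort 4 rule can assign women to an arm they can no longer receive, under either stated window, and the two windows contradict each other. That follows from the text and needs no assumption.

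The size does rest on even enrolment. About 7 of 100 allocations are affected under the better-supported 27 6/7 limit and about 19 under Table 4 as labelled; enrolment skewed to earlier gestation would lower both. The dilution figures also assume that the timing effect is the same size in all women enrolled before 26 weeks.

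The damage is confined to the randomised timing comparison in cohort 4. The descriptive booster objective and the primary analysis of cohorts 1 and 2 are unaffected. The point should be corrected, but it does not threaten the trial's main conclusions.

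**What to change.** In section 7.3.1, section 7 visit 1 and Table 4, limit cohort 4 randomisation to women for whom both allocations are still attainable on the day of randomisation. Register women already at 26 0/7 or later as a non-randomised later-boost group. Keep that group out of the before/after-26-week comparison and retain it for the descriptive booster objective.

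State one cohort 4 enrolment window in Table 4 and in both Appendix 4 schedules. The sponsor has to decide which was intended. If 34 0/7 is the limit for vaccination only, Table 4 should say so.

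The cost is protocol wording and one gestation check in the randomisation system. With even enrolment and 100 women in all, the randomised part falls to about 87 (100 × 91/105) under the 27 6/7 window or about 61 (100 × 91/148) under the 34 0/7 window. The women removed carry no information on the timing contrast, and undeliverable allocations fall to zero.
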